11.1.2. Dose-limiting Toxicities (DLTs)

DLT is defined as a treatment-related AE(s) occurring in Cycle 1 (including pre-dose assessments on Cycle 2 Day 1) that meets one of the criteria defined in the protocol. A summary table of DLTs will be presented for the dose escalation phase only by dose cohort including number and percentage of subjects having a DLT. The percentage of subjects having a DLT is based on the number of subjects in the DLT evaluable Population. DLT flag will be added to the listing of AEs.

In the dose escalation phase, a subject evaluable for DLT is defined as one who:

- Received at least 75% of the planned doses of CC-122 and of Nivolumab during Cycle 1 without experiencing a DLT, having been followed for the entire DLT assessment period (Days 1 to 28 of Cycle 1 including the pre-dose assessments specified for Day 1 of Cycle 2)

or

- Experienced a DLT after receiving at least one dose of either IP.

Non-evaluable subjects will be replaced at the discretion of the SRC. Additional subjects within any dose cohort may be enrolled at the discretion of the SRC.

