7.6. Definition of Dose-Limiting Toxicity

During dose escalation, the DLT assessment period is defined as Days 1 to 28 of Cycle 1 including the predose assessments specified for Day 1 of Cycle 2.

National Cancer Institute Common Terminology Criteria for Adverse Events (NCI CTCAE) Version 4.03 are used as a guide for the grading of severity of adverse events.

A DLT is defined as any of the following toxicities occurring within the DLT assessment window unless the event can clearly be determined to be unrelated to the drug. Dose-limiting toxicities are described below:

- Any toxicity that would lead to dose reduction or discontinuation of CC-122 or discontinuation of nivolumab during Cycle 1.
- Any Grade 4 non-hematologic toxicity of any duration.
- Any clinically relevant non-hematologic toxicity that is \geq Grade 3 except for:
 - Grade 3 diarrhea or vomiting of not more than 5 days duration (with optimal medical management)
 - Grade 3 fatigue or asthenia of not more than 3 days duration with optimal medical management
- Grade 3 infusion-related reaction controlled by interruption of the infusion and medical management Any liver enzymes elevation according to the definitions below:
 - AST or ALT ≥ 8 x ULN of > 7 days duration
 - Total bilirubin ≥ 5 x ULN of > 7 days duration
 - Concurrent AST or ALT > 3 x ULN and total bilirubin > 2 x ULN
- Hematological toxicities during Cycle 1 as follows:
 - Grade 4 neutropenia lasting > 7 days
 - Febrile neutropenia
 - Grade 4 thrombocytopenia lasting > 48 hours
 - Grade 3 or 4 thrombocytopenia with clinically significant bleeding
- Any \geq Grade 2 uveitis or eye pain that does not respond to topical therapy and does not improve to Grade 1 severity within the re-treatment period (≤ 6 weeks and/or prior to next nivolumab dose), or requires systemic treatment.

- Any \geq Grade 2 pneumonitis or interstitial lung disease that does not resolve with dose delay and systemic steroids. The management algorithm for pneumonitis or pulmonary toxicity can be found in the current nivolumab SmPC and in Appendix H.

Repeat laboratory assessments are required to confirm the duration of time-bound DLT criteria.

Isolated laboratory changes without associated clinical signs or symptoms (eg, hypomagnesemia, hypermagnesemia, hypoalbuminemia, hypophosphatemia, lymphocyte count increased or decreased) may not be included in this definition. These findings will be discussed and reviewed by the SRC.

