Events meeting the DLT definition occurring beyond the first cycle will be taken into account when determining the RP2D. Any AE with the potential to become a DLT based on the duration should be followed appropriately to accurately determine the duration of the event.

Subjects should delay/interrupt or discontinue treatment if they experience any adverse event, laboratory abnormality or intercurrent illness (regardless of causality) which, in the opinion of the investigator, presents a substantial clinical risk to the subject with continued dosing of any IP. Such delay/interruption or discontinuation, however, will not be considered a DLT unless it meets at least one of the DLT criteria defined above or if deemed dose-limiting by the SRC.

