10.2.3. Causality

The Investigator must determine the relationship between the administration of CC-122 and nivolumab and the occurrence of an AE/SAE as Not Suspected or Suspected as defined below:

- Not suspected: Means a causal relationship of the adverse event to IP administration is **unlikely or remote**, or other medications, therapeutic interventions, or underlying conditions provide a sufficient explanation for the observed event.
- Suspected: Means there is a **reasonable possibility** that the administration of IP caused the adverse event. ‘Reasonable possibility’ means there is evidence to suggest a causal relationship between the IPs and the adverse event.

Causality should be assessed and provided for every AE/SAE based on currently available information. Causality is to be reassessed and provided as additional information becomes available.

If an event is assessed as suspected of being related to a comparator, ancillary or additional IP that has not been manufactured or provided by Celgene, please provide the name of the manufacturer when reporting the event.

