4.2. Study Endpoints

Table 2: Study Endpoints

Endpoint	Name	Description	Timeframe
Primary Phase 1	The incidence of DLTs and the incidence and severity of treatment-emergent adverse events (TEAEs)	See Section 7.6 of protocol for the definition of DLTs	Dose Escalation Phase
Primary Phase 2	Preliminary efficacy as measured by ORR	The combined incidence of CR + PR, by investigator assessment of response by RECIST 1.1	Dose Escalation and Dose expansion Phase
Secondary	Preliminary efficacy	Disease control rate (DCR), duration of response (DoR), progression free survival (PFS), overall survival (OS), and time to progression (TTP) based on investigator assessment of response using RECIST 1.1 guidelines	Dose Escalation and Dose expansion Phase
Secondary	Plasma PK parameters	Including but not limited to maximum observed concentration (C_{max}), area under the concentration time curve (AUC), time to maximum concentration (T_{max}), terminal half-life ($t_{1/2}$), apparent total body clearance (CL/F) and apparent volume of distribution (V_z/F) for CC-122 and Nivolumab after multiple dose administration	Dose Escalation Phase
[REDACTED]	[REDACTED]	[REDACTED]	[REDACTED]
[REDACTED]	[REDACTED]	[REDACTED]	[REDACTED]
[REDACTED]	[REDACTED]	[REDACTED]	[REDACTED]

Endpoint	Name	Description	Timeframe
[REDACTED]	[REDACTED]		[REDACTED]

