11.1. Adverse Events

11.1.1. Summary of Adverse Events

AEs will be analyzed in terms of treatment-emergent adverse events (TEAEs) which are defined as any AEs that start between the date of first dose of study drug and 28 days after the last dose of CC-122 or 90 days after the last dose of Nivolumab, whichever is later. All AEs will be coded using the MedDRA[®] dictionary Version 21.0 or higher.

The incidence of TEAEs will be summarized by MedDRA SOC and PT. The intensity of AEs will be graded 1 to 5 according to the National Cancer Institute (NCI) Common Terminology Criteria for Adverse Events (NCI CTCAE) Version 4.03 or higher if possible. AEs that are not defined in the NCI CTCAE Version 4.03 or higher should be evaluated for severity/intensity according to Version 3.0. For all other AEs not described in the NCI CTCAE criteria, the intensity will be assessed by the investigator as mild (grade 1), moderate (grade 2), severe (grade 3), life-threatening (grade 4) or death (grade 5).

If a subject experiences the same AE more than once with a different grade, then the event with the highest grade will be tabulated in “by grade” tables. If a subject experiences multiple AEs under the PT (SOC), then the subject will be counted only once for that PT (SOC). In addition, AEs with a missing grade will be presented in the summary table as a grade category of “Missing” and will not be imputed.

A summary table of the subject incidence rate in each of the following categories will be provided. In addition, a table for each of the following categories will be produced where the incidence rate will be tabulated by SOC and PT and provided.

- TEAEs;
- TEAEs related to CC-122, Nivolumab and study drugs (CC-122 and/or Nivolumab);
- TEAEs of NCI CTCAE grade 3 or 4 by maximum NCI CTCAE grade;

- TEAEs related to CC-122, Nivolumab and study drugs (CC-122 and/or Nivolumab) with NCI CTCAE grade 3 or 4 by maximum NCI CTCAE grade;
- Grade 5 TEAEs with death outcome;
- Grade 5 TEAEs with death outcome related to CC-122, Nivolumab and study drugs (CC-122 and/or Nivolumab);
- Serious TEAEs;
- Serious TEAEs related to CC-122, Nivolumab and study drugs (CC-122 and/or Nivolumab);
- TEAEs leading to discontinuation of CC-122, Nivolumab and both study drugs (CC-122 and Nivolumab);
- TEAEs related to CC-122 leading to discontinuation of CC-122 and both study drugs (CC-122 and Nivolumab);

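### SAP 11.1.2 counts only treatment-related events as DLTs, while protocol 7.6, which the SAP cites for the same endpoint, counts a listed toxicity unless it is clearly unrelated

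*SAP*

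**What the plan says.** SAP 4.2, Table 2, makes DLT incidence one part of the Phase 1 primary endpoint. The other part is the incidence and severity of treatment-emergent adverse events (TEAEs). For DLTs the table says "See Section 7.6 of protocol for the definition of DLTs".

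Protocol 7.6 lists the toxicities and counts any of them in the assessment window "unless the event can clearly be determined to be unrelated to the drug". It gives the SRC two specific roles. On isolated laboratory changes without symptoms it says "These findings will be discussed and reviewed by the SRC". A delay, interruption or discontinuation made for substantial clinical risk is not a DLT "unless it meets at least one of the DLT criteria defined above or if deemed dose-limiting by the SRC".

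SAP 11.1.2 words the rule differently: "DLT is defined as a treatment-related AE(s) occurring in Cycle 1 (including pre-dose assessments on Cycle 2 Day 1". The sentence goes on to require that the event meet a criterion defined in the protocol. The same section takes the DLT percentage over the DLT evaluable set. A subject enters that set either by having a DLT after at least one dose, or by receiving at least 75% of the planned Cycle 1 doses of each drug with full follow-up and no DLT.

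Causality is collected under protocol 10.2.3: "The Investigator must determine the relationship between the administration of CC-122 and nivolumab and the occurrence of an AE/SAE as Not Suspected or Suspected". The scale has no third level.

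**The concern.** The two rules have different defaults. Under protocol 7.6 a listed toxicity counts, and only clear evidence of unrelatedness removes it. Under SAP 11.1.2, read literally, relatedness must first be present. Events of uncertain cause count under the first rule and may not count under the second.

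The SAP does not say how treatment-related is to be determined. A programmer would naturally use the causality field, because the neighbouring tables in SAP 11.1.1 are built on relatedness to either drug, for example "TEAEs related to CC-122, Nivolumab and study drugs (CC-122 and/or Nivolumab". The SAP would then report a DLT rate that does not follow the definition it cites. The visible items in SAP 15, which record changes as small as renaming the Treated Population, declare no change to the DLT definition.

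This matters because SAP 15, item 2, says the study will not enter expansion. DLT incidence is therefore part of the primary endpoint of the only phase that is run.

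**Working it through.** The plan states no figure on this point, so there is none to reproduce. The check compares the two rules and then illustrates the size.

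**Step 1: the causality scale.** Protocol 10.2.3 opens its lower level with "Not suspected: Means a causal relationship of the adverse event to IP administration is" and completes it with an improbable or remote relationship, or some other sufficient explanation. That is wider than clearly unrelated. No recorded level corresponds to the exclusion in 7.6.

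**Step 2: the two rules side by side.** Take a listed toxicity in the DLT window. Assume that treatment-related means Suspected for either drug, and that the drug in 7.6 means either drug.

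| Event | Protocol 7.6 | SAP 11.1.2 through the causality field |
|---|---|---|
| Suspected for either drug | DLT | DLT |
| Not suspected for both, but not clearly unrelated | DLT | not a DLT |
| Not suspected for both, and clearly unrelated | not a DLT | not a DLT |

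Only the middle row differs. On these assumptions the attribution rule makes the SAP count equal to or below the 7.6 count. On other readings of either phrase, the direction is not established.

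**Step 3: the denominator.** Planned CC-122 doses in Cycle 1 are 4 weeks x 5 days = 20 (protocol 7.2), and 75% of 20 is 15. A subject with 14 doses has 14/20 = 70% and is evaluable only by having a DLT. If the DLT is not counted, that subject leaves the evaluable set. This is plausible, because toxicity leading to discontinuation in Cycle 1 is itself a listed criterion in 7.6. For nivolumab two infusions are planned (Days 1 and 15, SAP 9.1). If the 75% is a count of infusions, one of two is 50% and falls short. The documents do not say whether it is a count or an amount, so that example is conditional.

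**Step 4: illustration with assumed counts.** Let x of n evaluable subjects have a DLT under 7.6, with one in the middle row. The reported rate is (x - 1)/n if the subject stays evaluable, and (x - 1)/(n - 1) if not. With n = 6:

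- x = 2: 2/6 = 33.3% becomes 1/6 = 16.7% (16.7 points lower) or 1/5 = 20.0% (13.3 points lower).
- x = 1: 1/6 = 16.7% becomes 0/6 or 0/5, both 0% (16.7 points lower).

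Two DLTs in up to six evaluable subjects is the threshold for a non-tolerated dose in protocol 7.4. In the x = 2 case the report would show one DLT at a dose that meets that definition.

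**The case against.** The strongest reply is that the SAP defers to the protocol twice, through the Table 2 reference and through the requirement to meet a protocol criterion. Treatment-related may then be shorthand for the 7.6 standard. Protocol usage lends this some support: 7.9 applies the clearly-unrelated wording to toxicity management and, two bullets later, calls certain treatment-related toxicities DLTs, while 7.10 speaks of IP-related toxicity that meets the DLT definition. Neither document says the DLT flag comes from the causality field. This stands as a reason to make the finding conditional. It does not remove the finding: on that reading the word adds nothing, and the SAP does not say it is meant that way.

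The consequences are also limited. The analyses are descriptive. A disputed event stays in the TEAE tables by grade and by cycle of onset and, where it applies, in the by-subject list of Grade 3 or 4 events. All of this stands.

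Three stronger readings are tempting and are not supported:

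- A reader might infer that protocol 7.9 contradicts 7.6. It does not. It says certain treatment-related events will be DLTs, and does not say that other events are not.
- A reader might infer that the SRC rules on the DLT status of every event. Its power in 7.6 to deem something dose-limiting covers delay, interruption or discontinuation, and its separate review covers isolated laboratory changes.
- A reader might infer that escalation could go wrong. Protocol 7.8 gives those decisions to the SRC, and the SAP's reporting rule does not govern them.

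**Conclusion.** The concern holds as a conflict between a stated SAP rule and the definition that the SAP cites. It should be corrected before the DLT table is produced. The conclusion depends on treatment-related being applied through the Suspected / Not suspected field. If it was meant as the 7.6 standard, the rules agree and only the wording needs repair.

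The size cannot be determined from the documents and is zero if no qualifying event was rated Not suspected. The protocol's amendment rationale mentions DLTs during escalation, and a reader might infer that some have been dropped. Nothing in the documents shows how any of them was rated. One affected subject in a cohort of six would lower the reported rate by 13.3 to 16.7 points in the cases worked above.

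A reader might also take this as a defect in the whole Phase 1 primary endpoint. It touches only the DLT part: the DLT table, the flag, the list of DLT events in SAP 11.1.1 that cites 11.1.2, and the evaluable denominator.

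**What to change.** In SAP 11.1.2, replace the treatment-related wording with the protocol 7.6 standard: a listed toxicity in the DLT window counts unless it is clearly determined to be unrelated. Base the DLT flag, the DLT table, the list of DLT events in SAP 11.1.1 and the DLT evaluable set on DLT status under 7.6, and not on the two-level causality field alone. Name the variable that holds this status. If a narrower rule is intended, declare it in SAP 15 and say how it is determined. This is a request for consistency with the cited definition and takes no view on which toxicities should be dose-limiting.

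The cost is a short SAP edit and a check that the named variable holds status under 7.6. The SAP mentions a DLT flag and a DLT term but does not say how either is filled. The reported DLT rate may be slightly less favourable. The treatment-related wording in protocol 7.9 can be aligned at the next amendment; the SAP edit does not depend on it.

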11.2. Clinical Laboratory Evaluations

Clinical laboratory results of interest include: chemistry (including troponin T and BNP), hematology (including PT/INR/PTT), immunology, thyroid functions and urinalysis. Clinical laboratory values will be graded according to NCI CTCAE version 4.03 or higher for applicable tests. Book or literature normal ranges will be used to determine the categories of High, Low, and Normal.

Lab results and change from baseline will be summarized by visit using descriptive statistics for continuous variables. Similarly, maximum and minimum post-baseline values and corresponding change from baseline values (including unscheduled visits) will be summarized using descriptive statistics.

Shift tables demonstrating the changes (low/normal/high) from baseline to worst post-baseline value will be displayed in cross-tabulations for categorical variables. Bidirectional shift tables (low and high) demonstrating the change of NCI CTCAE grades from baseline to worst post-baseline during the treatment period will also be presented. These will be presented in separate tables for low and high NCI CTCAE grades. Summaries of worst NCI CTCAE grade by cycle (up to and including cycle 6) and worst post-baseline NCI CTCAE grade will be provided.

Listings of clinical laboratory data with NCI CTCAE grades (if applicable) and abnormal flags (low or high) will be provided.

Listing of pregnancy status will be also provided.

For some key lab tests, spaghetti plots for individual subjects will be presented to show the pattern of the lab test values over time using the Safety Population. All non-missing lab test values including assessments at scheduled and unscheduled visits will be presented. The x-axis will be the scheduled visits, and the y-axis will be the exact values (unscheduled results will be associated with the scheduled visit they relate to). Value for the EOT visit will be included in spaghetti plots but will be displayed for the nominal visit equal to or immediately after the EOT visit. The mean plot lab test values for each dose cohort in the dose escalation part and for each subgroup in dose expansion part will also be provided.

11.3. Vital Sign Measurements

Vital sign values and change from baseline will be summarized using descriptive statistics for each visit. Similarly, maximum and minimum post-baseline values and corresponding change from baseline values (including unscheduled visits) will be summarized using descriptive statistics.

Shift tables demonstrating the changes (low/normal/high) from baseline to worst post-baseline value will be displayed in cross-tabulations. Normal ranges in [Table 9](#) will be used to determine the categories of low, normal and high. A listing of vital sign results will be provided.

Table 9: Normal Ranges of Vital Sign Measurements

Test	Normal Range (Unit)
DBP	[60, 90] (mmHg)
SBP	[100, 140] (mmHg)
Pulse	[60, 100] (bpm)
Temperature	[35, 38] (°C)

11.4. Electrocardiograms (ECG)

ECG parameters (from central review) and change from baseline with two-sided 95% CI will be summarized for each timepoint using descriptive statistics. Similarly, maximum and minimum post-baseline values (including unscheduled visits) and corresponding change from baseline values will be summarized using descriptive statistics.

Post-baseline abnormal QTc (both QTcF and QTcB) values will be summarized using frequency tabulations for the following 5 categories separately: QTc >450 msec; QTc >480 msec; QTc >500 msec; QTc increase from baseline >30 msec; QTc increase from baseline >60 msec.

Shift from baseline to worst post-baseline in the overall ECG interpretation ('Normal', 'Abnormal, not clinically significant' and 'Abnormal, clinically significant' by investigator review or 'Normal' and 'Abnormal' by central review) by visit will be displayed in cross-tabulations.

The mean change from baseline for each cohort along with the t-test 2-sided 95% CI, and the raw values for each individual subject will be plotted against scheduled/unscheduled visit to show the trend. Listings of ECG by investigator and central review will be provided.

11.5. Left Ventricular Ejection Fraction (LVEF) Assessment

LVEF assessment values and change from baseline will be summarized for each visit using descriptive statistics. Similarly, maximum and minimum post-baseline values (including unscheduled visits) and corresponding change from baseline values will be summarized using descriptive statistics.

Shift from baseline to worst post-baseline in the overall LVEF interpretation ('Normal', 'Abnormal, not clinically significant' and 'Abnormal, clinically significant') will be displayed in cross-tabulations. A summary table of abnormal LVEF will be provided. The following categories will be used in the summary:

- $\geq 20\%$ absolute drop from baseline in LVEF (%);
- $\leq 45\%$ in LVEF (%) at any post-baseline assessment;
- $\geq 20\%$ absolute drop from baseline in LVEF (%) or $\leq 45\%$ in LVEF (%) at any post-baseline assessment.

A listing of LVEF will be provided as well.

11.6. Ophthalmologic Exam

Data collected for ophthalmologic exam will be listed.

12. PK AND BIOMARKER ANALYSES

12.1. PK and Exposure Response Analyses

12.1.1. PK Parameters

PK parameters will be estimated based on the PK Population. Actual sampling times will be used in the calculations of PK parameters by using non-compartmental analysis (NCA). The following plasma PK parameters will be summarized for CC-122 and Nivolumab.

C_{\max}	Peak (maximum) plasma drug concentration
T_{\max}	Time to peak (maximum) plasma concentration at steady state
AUC_t	Area under the concentration-time curve calculated to the last observable concentration at time t
AUC_{inf}	Area under the concentration-time curve calculated from time zero to infinity.
V_z/F	Apparent volume of distribution during the terminal (λ_z) phase after extravascular administration
CL/F	Apparent clearance of drug from plasma after extravascular administration
$t_{1/2}$	Terminal elimination half-life

The following PK parameters will be also calculated for diagnostic purposes and listed but not be summarized.

λ_z	Terminal elimination rate constant (first-order)
λ_z lower	Lower limit of time (h) included in the calculation of λ_z .
λ_z N	Number of data points used in the calculation of λ_z .
λ_z upper	Upper limit of time (h) included in the calculation of λ_z .
Rsq adjusted	Adjusted regression coefficient for calculation of λ_z .
AUC %Extrap	Percentage of AUC_∞ due to extrapolation from the time of the last measurable concentration to infinity.

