Secondary	Preliminary efficacy	Disease control rate (DCR), duration of response (DoR), progression free survival (PFS), overall survival (OS), and time to progression (TTP) based on investigator assessment of response using RECIST 1.1 guidelines	End of Study
Secondary	Plasma pharmacokinetic (PK) parameters	Including but not limited to maximum observed concentration (C_{max}), area under the concentration time curve (AUC), time to maximum concentration (T_{max}), terminal half-life ($t_{1/2}$), apparent total body clearance (CL/F) and apparent volume of distribution (V_z/F) for CC-122 and nivolumab after multiple dose administration	End of Phase 1
[REDACTED]	[REDACTED]	[REDACTED]	[REDACTED]
[REDACTED]	[REDACTED]	[REDACTED]	[REDACTED]

Table 2: Study Endpoints (Continued)

Endpoint	Name	Description	Timeframe
[REDACTED]	[REDACTED]		[REDACTED]
[REDACTED]	[REDACTED]		[REDACTED]

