6.6.2. Pharmacokinetics of Nivolumab

Pharmacokinetic samples will be collected during the dose escalation part. No PK will be collected during the dose expansion part.

Dose Escalation Part (all subjects): Predose (-30 to -5 minutes prior to nivolumab dose) and end of infusion on C1D1 and C1D15.

6.7. 12-lead Electrocardiograms

Triplicate 12-lead ECGs will be recorded at the visits listed in Table 3 and assessed centrally. The 12-lead ECGs (12-lead at 25 mm/second reporting rhythm, ventricular rate, PR-interval, QRS complex, QT interval, and QTcF interval) will be performed after the subject has been in the supine position for at least 5 minutes.

Triplicate ECGs (3 recordings within 2 ± 1 minute intervals) will be performed at the following time points:

- Screening
- Cycle 1, Day 1 - Predose (0 hour; within 90 minutes prior to CC-122 dosing)

- [REDACTED]

[REDACTED]

■ [REDACTED]

[REDACTED]

[REDACTED]

■ [REDACTED]

[REDACTED]

[REDACTED]

[REDACTED]

[REDACTED]

[REDACTED]

■ [REDACTED]

[REDACTED]

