9.9. Other Topics

9.9.1. Assessment of Pharmacokinetics

Blood will be collected according to intensive and sparse sampling strategies to estimate the population PK of CC-122 when administered in combination with nivolumab.

Noncompartmental analyses will be performed using Phoenix WinNonlin Version 6.3 (Pharsight Corp., Mountain View, CA). The following PK measurements will be determined for CC-122 in subjects with intensive PK sampling:

- Area under the plasma concentration time-curve (AUC).
- Peak (maximum) plasma concentration (C_{max}).
- Terminal half-life ($t_{1/2}$).
- Time to maximum plasma concentration (T_{max}).
- Apparent total body clearance (CL/F).
- Apparent volume of distribution (V_z/F).

Sparse serum concentrations of nivolumab will be evaluated after the first dose administration with nivolumab and at steady state. Sparse concentrations of nivolumab will be summarized by descriptive statistics by cohort, visit and nominal time. If warranted, the impact of CC-122 on target mediated disposition of nivolumab will be assessed by non-mixed effect modeling (NMEM) compartment approach.

Descriptive statistics (N, mean, standard deviation, coefficient of variation (CV%), geometric mean, geometric CV%, median, minimum, and maximum) for plasma concentration and PK parameters will be provided. Correlations of drug exposure with safety, PD and clinical endpoints may also be analyzed as exploratory endpoints. Results will be presented in tabular and graphic forms as appropriate.

[REDACTED]

[REDACTED]

[REDACTED]

[REDACTED]

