12.1.2. Exposure vs. Dose

CC-122 and Nivolumab plasma concentrations will be summarized by phase, actual dose level (CC-122), visit, and nominal time points. Plasma PK parameters will be summarized by phase, actual dose level (CC-122) using descriptive statistics (N, mean, standard deviation, coefficient of variation [CV%], geometric mean, geometric CV%, median, min, and max). In general, geometric mean and the geometric CV (%) will be derived from non-zero concentration values.

Coefficient of variation CV (%) is calculated as follows: $100 \times (\text{standard deviation} / \text{mean})$.

Geometric CV (%) is calculated as follows: $CV (\%) = 100 \times \sqrt{\exp(\hat{\sigma}^2) - 1}$, where $\hat{\sigma}^2$ denotes the variance of the log-transformed values.

The following figures will be provided by actual CC-122 dose levels:

- Individual subject's concentration (linear scale) over time spaghetti plot;
- Individual subject's concentration (semi-logarithmic scale) over time spaghetti plot;
- Mean and \pm standard deviation of concentration (linear scale) over time plot;
- Mean and \pm standard deviation of concentration (semi-logarithmic scale) over time plot.

In addition, scatter plots of log transformed AUC_t , AUC_∞ , and C_{max} versus CC-122 dose will be presented.

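### SAP 12.1.1 plans terminal noncompartmental parameters for nivolumab that its sparse sampling cannot support, and SAP 17.6 would average a missing Day 15 trough as zero

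*SAP*

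**What the plan says.** **Sampling.** Protocol 6.6.2 takes nivolumab samples in dose escalation only: "Predose (-30 to -5 minutes prior to nivolumab dose) and end of infusion on C1D1 and C1D15". Nivolumab is given intravenously every 2 weeks, so C1D15 is the second infusion.

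**Parameters.** SAP 12.1.1 uses noncompartmental analysis (NCA) and says "The following plasma PK parameters will be summarized for CC-122 and Nivolumab". The list is Cmax, Tmax, AUCt, AUCinf, Vz/F, CL/F and t1/2, with Vz/F and CL/F defined for extravascular dosing. Adjusted R-squared and the number of points behind the terminal slope are listed as diagnostics.

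**Endpoint tables.** Protocol Table 2 promises these parameters "for CC-122 and nivolumab after multiple dose administration", and SAP Table 2 repeats this ("for CC-122 and Nivolumab after multiple dose administration").

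**Protocol analysis section.** Protocol 9.9.1 is narrower: "The following PK measurements will be determined for CC-122 in subjects with intensive PK sampling". For nivolumab it says "Sparse concentrations of nivolumab will be summarized by descriptive statistics by cohort, visit and nominal time", and then "If warranted, the impact of CC-122 on target mediated disposition of nivolumab will be assessed" by a modelling approach.

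**Concentration summaries.** SAP 12.1.2 already plans these: "CC-122 and Nivolumab plasma concentrations will be summarized by phase, actual dose level (CC-122), visit, and nominal time points". It adds that geometric means are in general taken over non-zero values.

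**Data handling.** SAP 17.6 gives the value zero to predose concentrations that are either below the limit of quantification (BLQ) or missing, for any visit and either drug. It includes zeros in the arithmetic mean, replaces a post-dosing zero by half the LLOQ for the geometric mean, and treats a zero that follows quantifiable values as missing when PK parameters are calculated. A BLQ value between quantifiable points is treated as missing.

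**The concern.** Nivolumab PK with CC-122 is a secondary objective. No PK is collected in expansion, so the escalation samples are all there will be.

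The parameter list asks of these samples something they cannot give. Either the nivolumab rows for t1/2, AUCinf, clearance and volume come out empty, or they rest on a line through two points, one of which is the peak. The apparent clearance and volume labels do not describe an intravenous drug either. The conflict starts in the protocol, where Table 2 and 9.9.1 disagree. The SAP follows the table, and the visible items of SAP section 15 do not address the point.

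The missing-value rule is a separate problem. Zero is sensible for a predose sample before any drug has been given. At C1D15 it records no drug 14 days after an infusion, merely because a tube is absent. C1D15 predose is the only nivolumab trough in the study, and cohorts are small.

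**Working it through.** The documents give no PK figure to reproduce, so the check is a count, a degrees-of-freedom argument and the arithmetic of a zero.

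**1. Points per dosing interval (protocol 6.6.2)**

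| Sample | Role |
|---|---|
| C1D1 predose | before any drug |
| C1D1 end of infusion | post-dose 1, first point |
| C1D15 predose | post-dose 1, second point (trough) |
| C1D15 end of infusion | post-dose 2, only point |

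**2. Terminal slope**

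Adjusted R² = 1 − (1 − R²)(n − 1)/(n − 2).

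- After dose 1, n = 2, so the divisor is 0 and the diagnostic is undefined.
- After dose 2, n = 1 and no slope exists. Hence no t1/2, AUCinf, clearance or volume can be had after multiple dosing.

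**3. How far a two-point slope can be off (illustration on assumed curves)**

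Estimated half-life = 14 × ln 2 / ln(C_end of infusion / C_Day 15 predose). Assumptions: a biexponential curve, distribution half-life 1 to 2 days, infusion length neglected, and a terminal phase carrying 40% to 80% of the end-of-infusion concentration.

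- Example: true half-life 21 days, share 80%. The Day 15 predose value is 0.8 × 2^(−14/21) = 0.504 of the peak, so the estimate is 9.70/0.685 = 14.2 days.
- Range for a true 21 days: 7.0 to 14.2 days.
- Range for a true 28 days: 7.7 to 17.1 days.
- Only an exactly monoexponential curve returns the true value.

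Steps 1 and 2 do not depend on these assumptions.

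**4. A missing C1D15 trough set to zero: arithmetic mean**

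With m of N missing, reported mean = (N − m)/N × mean of the observed values.

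- 1 of 6: 5/6 = 0.833, a fall of 16.7%.
- 1 of 3 or 2 of 6: 0.667, a fall of 33.3%.
- 1 of 20: 0.950, a fall of 5%.

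Protocol 7.8 takes escalation decisions at 3 or 6 evaluable subjects, and SAP 12.1.2 summarizes by dose level, so the first two lines are the relevant ones unless the SRC adds subjects.

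**5. The same zero: coefficient of variation**

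Let k = N − m observed values have mean 1 and CV c. Then variance = [(k − 1)c² + k − k²/N]/(N − 1), and reported CV = SD/(k/N).

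- 1 of 6, c = 30%: variance = (0.36 + 0.833)/5 = 0.239, SD 0.489, CV 0.489/0.833 = 58.6%.
- 1 of 6 with c = 20% or 40%: 53.5% or 65.1%.
- 2 of 6, c = 30%: 84.9%. 1 of 3, c = 30%: 92.3%.

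**6. The same zero: geometric mean**

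- Under SAP 12.1.2 the zero is left out, so there is no systematic change.
- Under SAP 17.6, if a C1D15 predose value counts as post-dosing, the reported value is (0.5/r)^(m/N) times the observed one, where r is the ratio of trough to LLOQ. For 1 of 6, r = 10 gives 0.05^(1/6) = 0.607 (−39.3%), and r = 100 gives 0.005^(1/6) = 0.414 (−58.6%). The range for r is assumed.

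**7. A BLQ C1D15 predose**

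Two SAP 17.6 rules apply to it. As a predose value it is zero. As a value between two quantifiable end-of-infusion points it is missing.

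**The case against.** The strongest reply is that little hangs on this. The PK analysis is descriptive, the visible exposure-response text concerns CC-122 only, and SAP 12.1.2 already delivers the nivolumab concentration summaries. The unsupported parameters would be surplus rows, and the listed diagnostics would show a reader that a slope had two points or none. The SAP also follows an endpoint table in the protocol. This limits the harm and stands as a reason for moderate weight. It does not cure a planned secondary endpoint that cannot be delivered.

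Section 15 of the SAP is partly redacted, and its item 3 moves some analyses from protocol 9.9 to separate reports. But the visible items run from 1 to 9 without a gap, and item 3 concerns exploratory objectives, whereas nivolumab PK is secondary.

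The two geometric-mean rules can be read in sequence: replace the zero by half the LLOQ, then average non-zero values. SAP 12.1.2 also says only in general. That is a possible reading, but the SAP does not state it, nor whether a C1D15 predose value is post-dosing. The BLQ overlap matters little if troughs lie well above the LLOQ.

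Finally, the sizes in steps 4 to 6 need a missing sample, and no missing rate is given. That is correct. PK parameters are also protected from the zero. The summary of the only trough is not.

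**Conclusion.** Both parts hold. With two points after dose 1 and one after dose 2, t1/2, AUCinf, CL/F and Vz/F for nivolumab cannot be validly estimated by NCA, and after multiple dosing they cannot be estimated at all. This follows from the sampling schedule alone. End-of-infusion concentrations, the C1D15 trough and a crude AUCt after dose 1 remain reportable.

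The zero rule biases the trough mean downward whenever a C1D15 predose sample is missing: by m/N exactly for the arithmetic mean, with a strongly inflated CV. The CV figures assume a true CV of 20% to 40%. The geometric-mean loss of 39% to 59% assumes a trough 10 to 100 times the LLOQ and the post-dosing reading of SAP 17.6. The same rule also reaches a missing CC-122 predose sample on C1D15.

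The consequences stay within descriptive secondary PK results. The text should be corrected, with no bearing on the primary endpoints.

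**What to change.** - **SAP 12.1.1 and SAP Table 2:** restrict the NCA parameter list to CC-122. For nivolumab, report end-of-infusion concentrations (C1D1, C1D15) and the C1D15 predose concentration, with modelling if warranted, as in protocol 9.9.1. Say where any modelling will be reported.
- **Protocol Table 2:** correct it to agree with protocol 9.9.1, or record the departure from it in SAP section 15.
- **SAP 17.6:** assign zero to a missing predose value only for the C1D1 (first-dose) sample. Leave later missing predose values missing, for both drugs. State one rule for a BLQ predose value after the first dose.
- **SAP 12.1.2 and 17.6:** keep one geometric-mean rule.

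The cost is a shorter nivolumab parameter list, a few sentences in the SAP, and either one section 15 entry or a minor protocol correction. No extra sampling is needed.
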